#### **TEAE occurring during the infusion or within 2 hours after the infusion:**

To determine whether a TEAE occurred within this time frame, information collected in two CRF forms will be considered: AE form (fields of onset date and time) and Drug Administration form (fields of administration date; start and end times; question 1 “Did the patient experience an AE during or after the infusion?” and the sub-questions in case the answer is Yes. The sub-questions are 1a: “During the infusion”, 1b: “Within 2 hours after the infusion” or 1c: “Up to 24 hours after the infusion”). Events which meet one of the following criteria will be considered to occur during infusion or within 2 hours after the infusion:

- Date and time for both TEAE and infusion are complete, and the onset of the TEAE is during the infusion or within 2 hours from its completion (stop time), regardless of the answer to question 1 above;
- The answer to question 1 above is Yes, and the options selected are either 1a or 1b.

All other events will not be classified into this time category.

### **10.3 Anti-Drug Antibodies (ADA)**

A summary table for IgG and Neutralizing antibody will present the number and percentage of patients who are positive or negative by visit. In case that IgG was tested twice on the same visit (for example, due to hypersensitivity) only the 1st test will be

part of the summary by visit. The table will also show the overall ADA status post-treatment where post-treatment positive is defined as positive in at least one visit post baseline (Visit 1), or negative if negative at all post-baseline visits, regardless of status at baseline.

Note that only patients who were tested positive for IgG ADA will be tested for Neutralizing Antibody. ADA characterization. i.e., IgG titer and positivity to other unique PRX-102 epitopes will be listed.

The decision about ADA status at each visit is based on sequential evaluation as follows:

1. If the IgG screening is negative then ADA at that visit is reported as “negative” (and no more evaluations).
2. If the IgG screening is “Presumptive Pos”, the next evaluation is the IgG Immunodepletion
  - a. If IgG Immunodepletion is negative then the ADA status at the visit is reported as “negative”
  - b. If IgG Immunodepletion is positive then the ADA status at the visit is reported as “positive”

Patients are considered treatment emergent ADA positive if they satisfy one of the following conditions:

1. Titer boosted: patients who were IgG positive to PRX-102 at baseline and boosted post treatment (i.e., titer increase by at least 4-fold from baseline. See Shankar et al. 2014 and FDA Guidance for Industry, January 2019: Immunogenicity Testing of Therapeutic Protein Products —Developing and Validating Assays for Anti-Drug Antibody Detection).
2. Treatment Induced: patients who were IgG negative to PRX-102 at baseline and positive in at least one timepoint post first infusion

The number and percentage of patients who are Treatment emergent ADA (yes/no) will be presented. For treatment emergent ADA, the table will indicate to which of the two groups a patient belongs (titer boosted or treatment induced).

A shift table from ADA status at baseline (positive or negative) to overall status post baseline (positive if positive in at least one visit post baseline, or negative if negative at all post-baseline visits).

## 10.4 Vital Signs

The vital signs (systolic and diastolic blood pressure, pulse rate, temperature, and respiration rate) will be summarized overall by visit. Within each visit, vital signs will be reported for pre-dose, 30 minutes from start of infusion, 60 min from start of infusion and then every hour up to 6 hours, and in addition the vital sign taken at the end of observation will be presented, regardless of the actual time they were taken (i.e. before or after 360 minutes). At each visit the change from pre-dose to each post dose will be presented. For the time points before 360 minutes, the analysis will use the nominal time in relation to the time of infusion.

In case that measurements are taken every 30 minutes or 60 minutes, but not at the planned times then only observations at 30, 60, 120... will be included in the analysis and the other will be listed (e.g. if measurements are taken at 15, 30, 45, 75, 105 minutes then the measurements at 15, 45, 75 and 105 will only be listed).

In case that patients do not tolerate the infusion, vital signs are taken every 15 minutes. These evaluations will only be listed.

In case the clinical visit lasted for more than 6 hours and vital signs were taken for more than 6 hours then these vital signs will only be listed.

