|---|---|------|----------------|----|----|----|----|----|----|----|----|-----|-----|-----|-----|-----|
| Activity /Visit Number/ Inf | S | V1 | 2w eek s | V2 | V3 | V4 | V5 | V6 | V7 | V8 | V9 | V10 | V11 | V12 | V13 | V14 |
| Quality of Life (5Q-5D-5L) | | x | | | | | | | x | | | | | | | x |
| Mainz Severity Score Index (MSSI) | | x | | | | | | | | | | | | | | x |
| Request patient approval by Medical Monitor | | x | | | | | | | | | | | | | | |
| Medical Monitor approval | | x | | | | | | | | | | | | | | |
| Echocardiography | | x | | | | | | | x | | | | | | | x |
| Cardiac function assessment (stress test) | | x | | | | | | | | | | | | | | x |
| Brain MRI | | x | | | | | | | | | | | | | | x |
| Adverse events assessments | | x | | x | x | x | x | x | x | x | x | x | x | x | x | x |
| Mutation analysis | | x | | | | | | | | | | | | | | |
| Con Meds | x | x | | x | x | x | x | x | x | x | x | x | x | x | x | x |
| Urine lyso Gb3 concentration | | x | | | x | | | x | | | | | x | | | x |
| Plasma Gb3 concentration ² | | x | | | x | | | x | | | | x | | | | x |
| Plasma Lyso Gb3 concentration ² | | x | | | x | | | x | | | | x | | | | x |
| Study Drug IV infusion ^{8,9} | | x | | x | x | x | x | x | x | x | x | x | x | x | x | x |
| Observe Patient ⁶ | | x | | x | x | x | x | x | x | x | x | x | x | x | x | x |
| Call Patient ⁷ | | x | | | | | | | | | | | | | | |

¹ Will be performed only for patients who have not had the test during the last 3 months before screening

² Will be performed pre-infusion

³ PK Time points: pre-infusion (baseline); 1 hour after the beginning of the infusion; at the end of the infusion, at 1 ± 0.25 , 2 ± 0.25 , 4 ± 0.25 , 8 ± 0.25 , 24 ± 0.5 , 48 ± 3 , and 96 ± 3 hours post-infusion and at 14 ± 3 , 21 ± 3 and 28 ± 3 days post-infusion

Patients who signed informed consent to this version (Version 4) before reaching Visit 7 (week 24), will perform PK at Visit 7; patients who signed informed consent after Visit 7 will perform PK at visit 11 (week 40).

⁵ Evaluate vital signs: blood pressure, pulse, temperature and respiration rate; any time pre-infusion, every 30 (±10) minutes during the first hour of the infusion, and from the second hour, 60 (±10) minutes up to the end of the clinical observation, and at the end of the observation time, if the patient tolerates the infusion. Otherwise, evaluate vital signs every 15 minutes until achieving tolerability.

⁶ According to [Appendix 8](#)

⁷ 24 hours post dosing first infusion

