14.8 Appendix 8. Schedule of Premedication, Infusion Rates, and Observation Times Post-Infusion

Proposed schedule to:

1. Taper down premedication
2. Increase infusion rate
3. Reduce observation time after infusion

The schedule below, will guide the sites on the process to taper down premedication, increase the infusion rate up to minimal time of infusion allowed by the protocol based on the tolerability of the patient, and reduce the observation time after infusion. At the end of the process, the patient may be offered to continue therapy in a home care setup based on the Investigator evaluation and discussion with the Medical Director.

General considerations:

1. Patients whose weight is up to (\leq)100 kg, the length of first infusion will be 4.5 hours.
2. Patients whose weight is more than ($>$) 100 kg, the length of first infusion will be 6 hours.
3. Clinical follow-up (observation) after the infusion in all rates will be 4 hours for the first infusion.
4. Patients who received the previous ERT with premedication will have the first infusion of pegunigalsidase alfa with the same protocol of premedication as with the previous ERT.
5. All changes can be implemented only if there is good tolerability of the previous change.
6. In the case of questionable tolerability, the continuation of the process will be discussed between the Investigator and the Medical Director.

1. Taper down premedication

The principle in the process is:

On the first infusion: the subject will continue the premedication as in previous ERT treatment. On the next infusion, one of the medications used as premedication will be removed. If well tolerated, on the next infusion, additional medication used as premedication will be removed (when applicable). This regimen will continue up to tapering down all premedications, or best tolerability to the infusion is achieved.

2. Reduce infusion time

The principle in the process is:

Reduction in the infusion time will start after an attempt was done to taper down the premedication based on patient tolerability. The length of infusion will be reduced by 0.5 hour as described in [Table 2](#) to achieve the best tolerated infusion length or an infusion of 2 hours (for patients \leq 100 kg weight) or 3 hours (for patients weighing more than 100 kg).

3. Reduce observation time after infusion

The principle in the process is:

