#### 10.2.2 Infusion Related Reactions (IRR)

IRRs are those TEAEs which occur during the infusion or within 2 hours after the completion of the infusion and their causality is definitely, probably, or possibly related.

Classification rules for assignment of patients with TEAEs during the infusion or within 2 hours after the infusion are described below.

Injection site reactions with SOC and PT listed in Table 2 are not considered IRR and should be excluded from the IRR analysis.

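### The only vital-sign table leaves out the 15-minute readings taken because an infusion is not tolerated, and most readings after 6 hours, so it can understate vital-sign change in poorly tolerated infusions

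*SAP*

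**What the plan says.** Vital signs are a named safety endpoint (SAP 3.2.1). SAP 10.4 summarises them by visit at pre-dose and then at "30 minutes from start of infusion, 60 min from start of infusion and then every hour up to 6 hours". The closing measurement of each visit is also tabulated, whatever its clock time. Change from pre-dose is given for each post-dose time.

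Three kinds of reading go to the listing only:

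- off-schedule readings: "only observations at 30, 60, 120... will be included in the analysis and the other will be listed";
- readings under close monitoring: "In case that patients do not tolerate the infusion, vital signs are taken every 15 minutes. These evaluations will only be listed";
- late readings, where the visit ran long and "vital signs were taken for more than 6 hours then these vital signs will only be listed".

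The trigger for close monitoring is in the Protocol flow chart (section 9.1, footnote 5). After setting the routine schedule for a tolerated infusion, it says: "Otherwise, evaluate vital signs every 15 minutes until achieving tolerability". Protocol Appendix 2 describes good tolerability as an infusion free of signs and symptoms, and names a change in vital signs among them.

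On visit length, Protocol Appendix 8 sets a first infusion of 4.5 hours (up to 100 kg) or 6 hours (over 100 kg), and adds: "Clinical follow-up (observation) after the infusion in all rates will be 4 hours for the first infusion". SAP 10.2.2 sets the period of interest for reactions: "IRRs are those TEAEs which occur during the infusion or within 2 hours after the completion of the infusion", subject to attributed causality.

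In SAP 13.1, Table 14.3.5 is the only vital-sign table. Section 12 states that safety variables get no shift tables. No summary of extremes is planned.

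**The concern.** A patient moves to 15-minute readings because the infusion is going badly, and altered vital signs are one of the ways it can go badly. Excluding those readings selects on something close to the outcome. The selection runs one way: the readings most likely to show a large change are the ones kept out.

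SAP section 12 says descriptive statistics include the minimum and maximum. An extreme reading that entered the table would therefore be visible even if it hardly moved the mean. An excluded one is visible only to someone reading Listing 16.3.3 line by line.

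The 6-hour limit raises a second question. The clock runs from the start of infusion, and the longest visits are the first ones after the switch, when premedication is being tapered and infusions shortened. The study's sample size is justified by the safety of switching, so the vital-sign table should not look calmer than the data.

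**Working it through.** The plan states no figure to reproduce. The check is a count of scheduled readings.

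**Inputs.** Infusion and observation hours by visit come from Protocol Appendix 8, Table 2. Readings fall at 30 min, 60 min, hourly from the start of infusion, and at the end of observation (Protocol 9.1, footnote 5). The tabulation rules are in SAP 10.4. The reaction window is infusion length plus 2 h (SAP 10.2.2).

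**Step 1: Visit 1.**

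- Up to 100 kg: 4.5 + 4 = 8.5 h. Post-dose slots are 0.5, 1, 2, 3, 4, 5, 6, 7, 8 and 8.5 h. Tabulated: 8 of 10; 7 h and 8 h are listed only. The reaction window ends at 4.5 + 2 = 6.5 h, so neither lost slot is inside it.
- Over 100 kg: 6 + 4 = 10 h. Slots are 0.5, then 1 to 10 h hourly. Tabulated: 8 of 11; 7, 8 and 9 h are listed only. The window ends at 6 + 2 = 8 h, so 7 h and 8 h, the two scheduled post-infusion slots inside it, are lost. The 6 h reading at the planned end of infusion is kept.

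**Step 2: all visits in Table 2.** A slot is lost if it is later than 6 h and is not the end-of-observation reading.

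| Weight | Premedications | Infusion + observation over 6 h | At least one slot lost | Slot lost inside reaction window |
|---|---|---|---|---|
| up to 100 kg | 0 | visits 1-3 | 1-2 | none |
| up to 100 kg | 1 | 1-4 | 1-3 | none |
| up to 100 kg | 2 | 1-5 | 1-4 | none |
| up to 100 kg | 3 | 1-6 | 1-5 | none |
| over 100 kg | 0 | 1-6 | 1-5 | 1-3 |
| over 100 kg | 1 | 1-7 | 1-6 | 1-4 |
| over 100 kg | 2 | 1-8 | 1-7 | 1-5 |
| over 100 kg | 3 | 1-9 | 1-8 | 1-6 |

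From visit 10 on, no column exceeds 6 h.

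**Step 3: 15-minute readings.** As an upper bound, assume close monitoring runs through a whole first infusion. That gives 4.5 × 4 = 18 or 6 × 4 = 24 readings, of which 5 (0.5, 1, 2, 3, 4 h) or 7 (0.5, then 1 to 6 h hourly) fall on nominal times. SAP 10.4 supports two readings:

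- Its third paragraph, taken literally, lists all of them: 0 of 18 or 0 of 24 tabulated.
- The worked example in its second paragraph keeps a value that falls on a nominal time. By that logic 5 of 18 or 7 of 24 are tabulated, and 13 or 17 are not.

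Either way most are excluded, and a programmer has no single rule to follow.

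**Step 4: a second wording conflict.** The first paragraph of 10.4 presents the end-of-observation reading whatever its time; the fourth sends readings after 6 h to the listing without exception. The counts above follow the first paragraph. If the fourth governed, every visit longer than 6 h would lose its last reading too.

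**The case against.** The strongest reply is that the table already covers what matters. The longest planned infusion is 6 h, so the grid of 30 min, 60 min and hourly to 6 h spans every planned infusion, and the end of observation is added. Listing 16.3.3 holds every reading. Reactions reported as adverse events are summarised as treatment-emergent events and as infusion-related reactions, by severity and preferred term. The study is descriptive, so no test or sample size changes. All of this stands, and it rules out several stronger readings that a reader might infer:

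- *That the table omits the periods in which drug-related change is expected.* It does not; it omits some readings from parts of those periods.
- *That tabulated values come only from tolerated infusions.* The 15-minute schedule lasts only until tolerability returns. Scheduled readings before and after it, and at the end of observation, remain.
- *That a fall in blood pressure after a first infusion would appear in no vital-sign table.* It would appear if still present at a tabulated time (5, 6 or 8.5 h up to 100 kg; 10 h over 100 kg). Only a transient change confined to excluded readings would be missed.
- *That nominal slots are misleading because the same clock time can be mid-infusion at one visit and post-infusion at another.* This is true of the clock, but SAP 10.4 plans change from pre-dose within a visit, not a comparison between visits or weight groups.

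The reply does not dispose of the selection itself. Event tables count what was reported, and the infusion-reaction tables also require attributed causality. Neither measures how far a vital sign moved. A listing is not a summary.

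**Conclusion.** The point holds in a limited form. Leaving the 15-minute readings out of the only vital-sign table is an informative exclusion, so tabulated changes from pre-dose can understate vital-sign change in poorly tolerated infusions. The 6-hour limit is a smaller matter. Inside the SAP's own reaction window it costs scheduled readings only above 100 kg, and only from visits 1-3 (no premedication) to visits 1-6 (three premedications).

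The size of the understatement cannot be stated. The documents do not say how often infusions are poorly tolerated or how many patients exceed 100 kg. The visit counts assume that Table 2 is followed; an infusion slowed or interrupted for intolerance could run past 6 h and widen the gap. The consequence is for descriptive safety reporting only.

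**What to change.** Keep the nominal-time table. Add to Table 14.3.5, for each visit, a summary of each patient's lowest and highest post-start value of each vital sign and the corresponding change from pre-dose. Use every reading: 15-minute, unscheduled and beyond 6 h. Show the number of readings beside these extremes, because a patient measured more often will tend to show a wider range.

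In the text of SAP 10.4, state (i) whether a 15-minute reading that falls on a nominal time is tabulated, and (ii) that the end-of-observation reading is tabulated even when taken after 6 h.

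The cost is SAP wording and programming; the readings are already collected.

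Two further additions may suggest themselves, but I would not require them. A table aligned to the end of infusion does not fit readings scheduled from the start: after a 4.5 h infusion they fall at about 0.5, 1.5, 2.5, 3.5 and 4 h, and observation later shrinks to 1 h. A count of systolic values at or below 90 mmHg would borrow a treatment threshold from Protocol Appendix 3 as an analysis cut-off; that is optional.

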## 10.5 Laboratory Test Results

The following laboratory test results will be summarized overall by descriptive statistics at the scheduled visits, and for continuous results also including the change from baseline:

1. Hematology: Hemoglobin, Platelets, Total white blood cell count
2. Coagulation Profile: Partial thromboplastin time (PTT), Prothrombin time (PrT)
3. Vitamin D
4. Urinalysis: Dipstick for presence of blood, Dipstick for presence of glucose, Dipstick for presence of ketones, Dipstick for presence of Protein
5. Biochemistry: Alanine transaminase, Albumin, Alkaline phosphatase, Aspartate transaminase, Bilirubin (total), Blood urea nitrogen, Calcium, Creatinine, Creatine phosphokinase, Cystatin c, Gamma-glutamyl transferase, Glucose,

Lactate dehydrogenase, Phosphate (inorganic), Potassium, Sodium, Total protein and Uric acid

Note: serum creatinine can be recorded in two units,  $\mu\text{mol/L}$  and  $\text{mg/dL}$ . In calculation of eGFR or summary of creatinine, the value in  $\mu\text{mol/L}$  needs to be converted to  $\text{mg/dL}$  using the following conversion formula:  $1 \text{ mg/dL} = 88.4 \mu\text{mol/L}$ .

Note: Serum creatinine can be entered in two fields in the Study Data Tabulation Model (SDTM) (CHEMISTRY and ENZYMADE). When the results from same sample is entered at both fields, then the value is identical. In such cases, only one of them will be taken in the analysis

In case that blood sample is taken twice at the same visit, only the results of the first blood sample (based on the time the blood sample was taken) will be listed and used in the analyses.

All laboratory results will be listed (also parameters that are not tabulated).

For parameters for which, there are test results which are below the level of detection and reported with ' $<$ ' sign, the change from baseline analysis will not be presented. The analysis of actual values at the visit will be based only on the values for which the true value was observed, and the summary will indicate the number of observations that were below the limit of detection. In the listings, these observations will be presented with the ' $<$ ' sign.

## 10.6 Physical Examination

The physical examination results (normal / abnormal / not done) will be summarized overall by body system and by visit.

## 10.7 Electrocardiography (ECG)

Descriptive statistics for the following quantitative and qualitative ECG parameters will be summarized by visit overall. For quantitative parameters, the change from baseline will be summarized as well.

1. Quantitative ECG parameters: Mean Heart Rate, PR Interval (Aggregate), QRS duration (Aggregate), QT Interval (Aggregate)

2. Qualitative ECG parameters: Rhythm – Normal Sinus Rhythm (NSR), Conduction abnormalities, Left ventricular hypertrophy, Supraventricular tachycardia, Premature atrial contraction, Atrial flutter, Atrial fibrillation, Premature ventricular contraction, Ventricular tachycardia, and Any clinically abnormal findings (i.e. any abnormal condition as listed above).

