- Investigator feels that it is not in the best interest of the patient to continue treatment and/or if the Investigator believes that the patient can no longer be compliant with the requirements of the study.

SAFETY ENDPOINTS:

Changes from baseline in:

- Clinical laboratory tests
- Physical examination
- Assessment of the injection site
- Electrocardiogram
- Treatment-emergent adverse events
- Ability to taper off infusion premedication
- Requirement for use of premedication overall to manage infusion reactions
- Treatment-induced anti-pegunigalsidase alfa antibodies

EFFICACY EXPLORATORY ENDPOINTS:

- Estimated glomerular filtration rate (eGFR_{CKD-EPI})
- Left Ventricular Mass Index (g/m²) by echocardiogram
- Plasma Lyso-Gb3
- Plasma Gb3
- Urine Lyso-Gb3
- Protein/Creatinine ratio spot urine test
- Frequency of pain medication use
- Exercise tolerance (Stress Test)
- Short Form Brief Pain Inventory (BPI)
- Mainz Severity Score Index (MSSI)
- Quality of life EQ-5D-5L

PHARMACOKINETICS (PK): Blood samples from all patients will be taken for PK analysis on Day 1 and at the end of treatment at Visit 14 (week 52). Blood samples will be drawn for an additional intermediate PK analysis at Visit 7 (week 24), for all patients who signed informed consent to this version (Version 4) before reaching Visit 7 (week 24), or at Visit 11 (week 40) for patients who passed Visit 7 at the time of signing the informed consent to this version. The following (but not limited to) PK parameters will be derived from the plasma concentration *versus* time profiles to determine the PK of the study drug: C_{max}, T_{max}, t_{1/2}, AUC_{0-t}, and AUC_{0-∞}. Blood samples will be drawn at the following time points: pre-infusion (baseline); 1 hour after the beginning of the infusion; at the end of the infusion, at 1±0.25, 2±0.25, 4±0.25, 8±0.25, 24±0.5, 48±3, and 96±3 hours post-infusion and at 14±3, 21±3 and 28±3 days post-infusion

before next infusion (a total of 13 timepoint within 28 days).

STATISTICAL ANALYSIS:

The sample size of approximately 30 patients is adequate to evaluate the safety of switching from agalsidase alfa and agalsidase beta to pegunigalsidase alfa in Fabry disease in which patient recruitment in clinical trials is difficult.

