8.3 Safety Variables

Safety will be assessed by changes from baseline in:

- Clinical laboratory tests
- Physical examination
- Assessment of the injection site
- Electrocardiogram
- Treatment-emergent adverse events
- Ability to taper off infusion premedication throughout the first 2 months of the study
- Requirement for use of premedication overall to manage infusion reactions

- Treatment-induced anti-pegunigalsidase alfa antibodies ([Appendix 3. Pegunigalsidase alfa Hypersensitivity Evaluation and Treatment Algorithm](#))

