10.3 Analysis

Demographics. For continuous variables, n, mean, standard deviation, median, minimum, and maximum will be presented. For categorical variables, frequency counts and percentages will be presented.

Medical History, Vital Signs, and Physical Examination. For medical history, frequency count by treatment will be provided for each body system.

For physical examination, frequency count of normal or abnormal by treatment will be tabulated for each body system.

Medications. Summary and/or data listings of the prior, concomitant medication, and class of medication will be provided.

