10.3.2.2 Clinical Laboratory

Clinical Laboratory examinations will be performed prior to and during treatment.

Descriptive statistics will be presented for the value and abnormality of each of the clinical laboratory results by visit and dose group. Shift tables describing abnormality shifts from baseline to after treatment and follow-up will be created.

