## **12. DIFFERENCES FROM PROTOCOL**

The statistical section of the protocol is short and was not meant to provide detailed information for the analysis. Some of the changes in the planned analysis of PB-102-F50 are due to knowledge and insights gained in the overall clinical program of PRX-102.

The main changes in the analysis plan compared to protocol are as follows:

1. The following endpoints were added: Infusion Related Reaction (IRR) and Fabry clinical events.
2. Analysis sets: the protocol defined the Intent-to-Treat as the main efficacy set. The SAP revised the main efficacy set to be called Efficacy population. It differs from the Intent-to-Treat proposed in the protocol that requires that a patient should have at least one post

baseline observation. The Per-Protocol set was removed since there is no primary endpoint and no sensitivity analysis is planned.

3. Efficacy variables: the protocol specified that the percent change from baseline will be used for quantitative efficacy endpoints. The SAP revised this, and depending on the endpoint, either a change from baseline or percent change from baseline or both are being used. For some of the efficacy end-point, only a shift table is presented.
4. Descriptive statistics for all variables include: mean (SE), SD, median, minimum and maximum. The interquartile range is not presented.
5. No shift tables are used for safety variables.
6. Evaluation of Acute Kidney Injuries is based on AE reporting and clinical judgment of the investigator and not by independent nephrologists.
7. 95% CI; Shift tables were added for some efficacy.
8. The statistical section of the protocol stated that hypersensitivity will be analysed as AE of special interest. Since IRR is a wider analysis which was added (see item 1 in this list), then the analysis of hypersensitivity will be part of the IRR evaluation.

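### No planned summary table counts new qualitative ECG abnormalities, although the protocol assesses ECG safety by change from baseline

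*SAP*

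**What the plan says.** Protocol section 8.3 introduces its list of safety variables with "Safety will be assessed by changes from baseline in", and the synopsis heads the same list with "Changes from baseline in". Both lists include physical examination and electrocardiogram.

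SAP 10.7 states: "Descriptive statistics for the following quantitative and qualitative ECG parameters will be summarized by visit overall". It continues: "For quantitative parameters, the change from baseline will be summarized as well". The quantitative parameters are heart rate, PR, QRS and QT. The qualitative ones are sinus rhythm, conduction abnormalities, left ventricular hypertrophy, supraventricular tachycardia, premature atrial and ventricular contractions, atrial flutter, atrial fibrillation, ventricular tachycardia, and a row for any of these abnormalities.

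For physical examination, SAP 10.6 says: "The physical examination results (normal / abnormal / not done) will be summarized overall by body system and by visit". Here the protocol's analysis section (10.3) already planned the same kind of display: "For physical examination, frequency count of normal or abnormal by treatment will be tabulated for each body system".

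The SAP table list holds one table for physical examination (14.3.7) and two for ECG (14.3.8.1 quantitative, 14.3.8.2 qualitative). None is titled as a shift or incidence table. SAP section 12 item 5 declares, as a difference from the protocol: "No shift tables are used for safety variables".

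**The concern.** The study has one arm and no planned tests, so each patient's own baseline is the only comparator. For a yes/no finding, change from baseline means knowing who acquired it and who lost it. A count at each visit gives only the margins of that cross-classification.

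The any-abnormality row has a further limit. A patient with a persistent abnormality at baseline is counted in it at every visit, so that row cannot register a second, new abnormality in the same patient.

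What is at stake is whether the report's tables answer a safety endpoint that the protocol names. The sample size is justified only as adequate to evaluate the safety of switching. A reader of the ECG table will want the number of patients with a new finding, and the planned table does not give it.

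**Working it through.** There is no stated figure to reproduce: the sample of 30 (SAP 4.1) is pragmatic, and the documents give no prevalence of ECG findings and no dropout rate. The check is a bound on a paired two-by-two table, followed by a comparison of the other planned outputs.

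**Step 1: what per-visit counts allow.** Let n patients be assessed at both visits, m1 with the finding at baseline and m2 with it later. Then

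- minimum new cases = max(0, m2 − m1)
- maximum new cases = min(m2, n − m1)

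With n = 30 and assumed counts:

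| m1 | m2 | New cases possible |
|---|---|---|
| 3 | 3 | 0 to 3 |
| 6 | 6 | 0 to 6 |
| 6 | 8 | 2 to 8 |
| 10 | 8 | 0 to 8 |
| 10 | 10 | 0 to 10 |

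In the 6-and-6 case, 30 − 6 = 24 patients are free of the finding at baseline, so the range is 0/24 = 0% to 6/24 = 25%. The 25% arises only if all six baseline findings resolve while six other patients acquire it.

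**Step 2: where the ambiguity disappears.** If m1 = 0, both bounds equal m2, so the count at a visit is the number of patients with a new finding present at that visit. The problem concerns findings already present in some patients at baseline.

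**Step 3: the any-abnormality row.** Take a patient with left ventricular hypertrophy at baseline that persists, who later shows atrial fibrillation. The any-abnormality row is unchanged. Atrial fibrillation has its own row, which gains one patient unless another patient's atrial fibrillation has resolved by that visit.

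**Step 4: other routes to a new finding.**

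- *Listing 16.3.6 (ECG).* The SAP says listings present all collected data, so each later ECG can be compared with Visit 1 by hand.
- *Adverse events.* Protocol 8.3.1 counts worsening of a pre-existing condition as treatment-emergent. It requires clinically significant laboratory abnormalities to be recorded as adverse events but states no matching rule for ECG findings, so capture depends on the investigator.
- *Fabry clinical events (SAP 9.13, Table 14.2.12).* The criteria include atrial fibrillation, ventricular tachycardia, and pacemaker or defibrillator implantation. They do not name atrial flutter, supraventricular tachycardia, premature contractions, conduction abnormality or left ventricular hypertrophy.
- *Mean change in PR and QRS.* This may move with conduction disease but does not count affected patients.

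**Step 5: consistency of section 12 item 5.** Item 5 says no safety shift tables are used. Yet the list contains two: Table 14.3.4.2 (antibody status) and Table 14.3.9.3.2 (premedication). The SAP also plans baseline shifts for qualitative cardiac data elsewhere: valve assessments (9.7) and the stress test (9.9).

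**The case against.** The best defence is that this is a declared choice in a small descriptive study. The SAP governs where it differs from the protocol, and item 5 states that safety shift tables are not used. The synopsis asks only that safety endpoints be compared with baseline by summary statistics, which a by-visit table including baseline does in a loose sense. The change-from-baseline heading is generic: it also covers adverse events and premedication tapering. The protocol names shift tables only for laboratory data: "Shift tables describing abnormality shifts from baseline to after treatment and follow-up will be created". With 30 patients, the listings can be read.

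Much of this stands, and it rules out several stronger readings:

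- A reader might infer that new arrhythmia or conduction disease cannot be told from pre-existing disease at all. The documents do not support that; Step 4 gives the other routes.
- A reader might infer that the SAP departs from the protocol's planned analysis of physical examination. It does not: protocol 10.3 plans frequency counts. The mismatch lies partly inside the protocol, between its endpoint wording and its analysis section.
- A reader might link this to arrhythmia as a sign of severe hypersensitivity in Appendix 3. That is an acute reaction monitored around the infusion, a different assessment from the scheduled ECGs.
- A reader might suppose that patients who leave early drop out of the comparison. Protocol 6.3.3 and 9.2.9 ask sites to attempt the Visit 14 tests at withdrawal, so the loss may be partial.

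The precedence rule does not close the gap. It settles which text is followed, not whether the table answers the endpoint. Item 5 gives no reason, does not say that change from baseline is dropped for ECG, and is contradicted by the SAP's own table list.

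**Conclusion.** The point holds for the summary tables: no listed table identifies new-onset qualitative ECG findings, although the protocol places ECG under change from baseline. New findings can be found only from Listing 16.3.6, adverse event reports or, for atrial fibrillation, ventricular tachycardia and device implantation, Fabry clinical events. Physical examination shares the limit but is secondary, because SAP 10.6 follows protocol 10.3.

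The size cannot be estimated from the documents. The range of 0 to 6 new cases rests on assumed counts of 6 of 30 at both visits and complete follow-up; it illustrates the ambiguity and is not a forecast. The conclusion also assumes that neither SAP 7.1, whose text was not available for this assessment, nor the separate table shells contains a general rule adding baseline comparisons for categorical variables. Section 12 item 5 and the table titles point against one. The change is worth making because it is specific, inexpensive and bears on a named safety endpoint.

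**What to change.** - In SAP 10.7 and Table 14.3.8.2, add for each qualitative ECG abnormality the n (%) of patients with the finding at any post-baseline visit, among those without it at baseline and with at least one post-baseline ECG. For sinus rhythm, the normal state, count loss of it among those who had it at baseline.
- Define any new abnormal ECG finding as at least one listed condition that was absent at baseline, so that patients already abnormal can still contribute.
- Optionally, add the same column by body system in Table 14.3.7.
- Correct section 12 item 5 so that it agrees with Tables 14.3.4.2 and 14.3.9.3.2, and state there how qualitative ECG and physical examination are compared with baseline.

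The cost is SAP wording and an added column in one or two tables. ECG and physical examination are already scheduled at Visits 1, 4, 7, 11 and 14, so no new data are needed. This changes reporting only and leaves clinical management untouched.
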